##### 2.1.2.11.1.2 AE and ADR by severity

The number of events, the number of patients who developed AEs or ADRs and the proportion will be summarized by treatment group, by SOC and PT, and by severity. If the same event occurred more than once in the same patient, the number of patient will be counted only once for the most severe event.

##### 2.1.2.11.1.3 Death, SAEs

A list of deaths and SAEs will be prepared.

##### 2.1.2.11.1.4 Significant AEs

A significant AE includes a non-serious AE leading to discontinuation of the study drug and regarded as a non-SAE that is considered to be of special interest due to its clinical significance. A list of significant AEs will be prepared.

### 2.1.2.11.2 Laboratory test

- (1) Analysis set : SP
- (2) Analysis item : measured values and changes (each time point - Day 0).

Test item :

< Hematology >

Red blood cell count, white blood cell count, differential white blood cell count (neutrophils, lymphocytes, monocytes, eosinophils, basophils), platelet count, hemoglobin, hematocrit

< Blood chemistry >

Total protein, albumin, AST (GOT), ALT (GPT),  $\gamma$ -GTP, ALP, LDH, CK (CPK), total bilirubin,

total cholesterol, HDL-cholesterol, LDL-cholesterol, triglycerides (TGs), BUN, creatinine, blood glucose, Ca, Na, K, P, Cl

< Urinalysis >

Qualitative analysis (occult blood, protein, sugar, urobilinogen)

< Pregnancy test >

Qualitative analysis (urinary hCG or serum hCGs)

(3) Time point: Day 0, Day 5, at discontinuation/completion of treatment

\*If more than one test value prior to administration including the value at Unscheduled visit are obtained, the value immediately prior to administration will be used as that on Day 0 (baseline).

(4) Analytical method :

1) Summary statistics (number of patients, mean, standard deviation, minimum, median, maximum) for the measurement values and changes in each parameter of the blood test will be calculated by treatment group and by time point.

2) A chart for the measurement values of each parameter of each blood test over time in each patient will be prepared by treatment group. Box-and-whisker plots for summary statistics will be also prepared.

3) The number of patients and the proportion based on the qualitative data of each parameter in urinalysis will be summarized by treatment group and by time point (number of subjects, %)

4) A list of measured values outside the reference range of the institution will be prepared.

5) A list of laboratory test data will be prepared. Analysis set : Randomized Patients

6) A list of laboratory reference values of the institution will be prepared. Analysis set : Randomized Patients

#### 2.1.2.11.3 Vital signs

(1) Analysis set : SP

(2) Analysis item : measured values and changes (each time point - Day 0)

Test parameter : blood pressure (systolic, diastolic), pulse rate, temperature, respiratory rate

(3) Time point : Day 0, Day 5, at discontinuation/completion of treatment

(4) Analytical method :

1) Summary statistics (number of patients, mean, standard deviation, minimum, median, maximum) for each measured values and changes will be calculated by treatment group and by time point.

2) A chart for measured values of each parameter over time in each patient will be prepared by treatment group.

3) A list of measured values outside the reference range in each institution will be prepared.

4) A list of data on vital signs will be prepared. Analysis set : Randomized Patients

#### 2.1.2.11.4 Resting 12-lead electrocardiogram (ECG)

(1) Analysis set : SP

(2) Analysis item : measured values

Test parameter : heart rate

(3) Time point : Day 0, Day 5, at discontinuation/completion of treatment

(4) Analytical method :

1) A chart for measured heart rates of each patient over time will be prepared by treatment group.

- 2) The number of patients and the proportion based on presence or absence of ECG abnormality will be summarized by treatment group and by time point (number of patients, %).
- 3) A list of resting12-lead ECG findings will be prepared. Analysis set : Randomized Patients

#### **2.1.2.12 Interval estimation and level of significance**

As a general rule, the significance level of 5% two-sided will be applied, and a two-sided 95% confidence coefficient ( $1-\alpha$ ) will be applied for the interval estimation.

[figure not shown]
#### **2.1.2.13 Multiple comparison and multiplicity**

Multiplicity will not be considered.

#### **2.1.2.14 Handling of missing data, unspecified observations and other inappropriate data**

- (1) If a measurement error or another artificial error in the laboratory measurement has been scientifically proven, the re-measurement result will be adopted.
- (2) If the cause of an abnormal data is not clear, the data will be used for evaluation.
- (3) If any missing data not specified above are found, consultation with the medical expert will be conducted as necessary, and handling of those data will be discussed at the Case Review Committee before data fixation.
- (4) If any categorical variables in the efficacy endpoint are missing until the date of completion or discontinuation of the study, the missing category will be set and the data will be summarized after the values have been included in the denominator.
- (5) Handling of data on arterial blood-gas analysis (A-aDO2, PaO2, PaCO2, pH) at discontinuation/completion of treatment  
If the actual date of discontinuation/completion of treatment is Day 1, Day 3, Day 5, or Day 10 from the start of treatment, then the data on the day will be regarded as the data at the time in the analysis.

(6) Arterial blood gas analysis will be handled as shown below

#### 2.1.2.15 Subgroup analysis

A subgroup analysis for the analysis defined in Section “2.1.2.10.1 primary endpoint” will be performed (only in the FAS). The factors for subgroup are as follows.

- Sex
- Age (<65 years,  $\geq 65$  years)
- With or without concomitant use of antiviral drugs for COVID-19 (excluding Cox's proportional hazards model)
- Class of steroid used (dexamethasone, methylprednisolone or prednisolone, other [mixture of dexamethasone and methylprednisolone or prednisolone])
- Baseline category on a 7-point ordinal scale (3/4/5)

A subgroup analysis for the analysis defined in 2) of Section “2.1.2.11.1.1 AE and ADR” will be performed. The factors for subgroup are as follows.

- Sex
- Age (<65 years,  $\geq 65$  years)
- With or without concomitant use of antivirals drugs for COVID-19

#### 2.1.2.16 Exploratory analysis

Refer to Section 2.1.2.10.2.10

#### **2.1.2.17 Interim analysis**

Not applicable.

### **3 Changes to conduct of the study or planned analysis (Section 9.8 of Clinical Study Report)**

Not applicable.

### **4 Technical details contained in the analysis methodology document (Section 16.1.9 of the Clinical Study Report)**

#### **4.1 Handling of dating**

##### **(1) Handling of incomplete dating and calculation of the period**

Relevant data will be reviewed in the Case Review Committee.

##### **(2) Handling of "discontinuation" and "unspecified examination"**

If an examination has been conducted as an examination on the specified Visit, the data will be included in the analysis as the data on the specified Visit. Otherwise, they will not be included in the analysis.

Handling of those data will be examined in the Case Review Committee. All the data including those at discontinuation or unspecified examinations will be outputted in the listing.

#### **4.2 Unit and detection limit**

The unit and reference values for the laboratory test and vital signs will be used as those in the institution, and not be converted.

If any BLQ (Below the lower limit of quantification) or ALQ (Above the upper limit of quantification) values are included in the measured values for cytokine markers, the following lower limit and upper limit will be complemented.

IL-6 : 4.07 pg/mL - 990.00 pg/mL

IL-1 $\beta$  : 16.42 pg/mL - 3990.00 pg/mL

TNF- $\alpha$  : 7.33 pg/mL - 1780.00 pg/mL

IL-10 : 12.72 pg/mL - 1030.00 pg/mL

CCL17 : 104.40 pg/mL - 25370.00 pg/mL

CXCL9 : 709.14 pg/mL - 172320.00 pg/mL

MMP-12 : 47.61 pg/mL - 11570.00 pg/mL

\*Based on the final report of the "Validation study of concentration measurement method of cytokines in human serum (M20-0182-02)".

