5.2 Endpoints

5.2.1 Efficacy endpoints

Primary efficacy endpoint

Number of days to achieve at least 2-rank improvement on a 7-point ordinal scale from baseline until Day 28.

[Rationale]

A 7-point ordinal scale is one of the commonly used scales for assessment of drugs used in the clinical studies of COVID-19 and was set as an index to numerically assess the improvement effect of sargramostim administration on the disease condition. Taking the study drug administration period (5 days, in principle [up to 10 days]) in this study, the usual period for treatment and hospital stay of COVID-19 patients in Japan, and the results of other clinical studies into account, the required number of days to achieve at least 2-rank improvement on a 7-point ordinal scale from baseline until Day 28 was set as the primary efficacy endpoint.

Secondary endpoints

- (1) Changes in alveolar-arterial oxygen partial pressure gradient (A-aDO₂) from baseline to Day 5 and the end of administration.
- (2) Number of days until discharge from baseline (days for shifting to Category 7 on a 7-point ordinal scale).
- (3) Proportion of subjects whose category has shifted to Category 1 or 2 on a 7-point ordinal scale from baseline until Day 28.
- (4) Changes in pulmonary inflammatory findings from baseline to Day 5 and the end of administration.
- (5) Changes in arterial blood-gas parameters (partial pressure of oxygen [PaO₂] and partial pressure of carbon dioxide [PaCO₂]) from baseline to Day 5 and the end of administration.
- (6) Changes in inflammatory markers and cytokines from baseline to the end of administration.
- (7) Distribution and proportion of each category on 7-point ordinal scale on Day 14 and Day 28.
- (8) Distribution and proportion of each category of oxygen requirement until Day 14.
- (9) Other exploratory items (details will be specified separately in the statistical analysis plan).

[Rationale]

- (1) An interim analysis of the clinical study ¹¹ being conducted in Belgium in COVID-19 patients (20/ target sample size of 80) suggested the efficacy of sargramostim for A-aDO₂, an index of arterial oxygen uptake (see 6.3 Rationale for dosage and administration). Therefore, changes in A-aDO₂ was set as a secondary endpoint in this study. Since the duration of the study drug administration in this study is set to be "5 days, in principle (up to 10 days)", both the periods of "Day 5 from baseline" and "End of administration from baseline" were set for assessment.

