13.6 Laboratory tests (blood chemistry, hematology, urinalysis, and pregnancy test)

The following items will be measured at the medical institution. If the measurement results deviate from the reference value, the investigators will assess whether the deviation is clinically significant. Pregnancy test will be performed only for women of childbearing potential. Pregnancy test will not necessarily be required for a female subject considered unable to become pregnant due to the following reasons: menopause (amenorrhea for at least 12 months without medical reasons), total hysterectomy, or that she does not get the first menstruation yet. The date of the sample collection and the test results will be entered in the eCRF.

Abnormal changes in laboratory test values that are judged by the investigators to be applicable to adverse events will be reported separately as adverse events (see "14.1 Definitions of AE").

Table 13.6-1 List of Laboratory Parameters

Hematology	Red blood cells count, white blood cells count, differential white leucocytes (neutrophils, lymphocytes, monocytes, eosinophils, basophils), platelets count, hemoglobin, hematocrit
Blood chemistry	Total protein, albumin, AST (GOT), ALT (GPT), γ -GTP, ALP, LDH, CK (CPK), total bilirubin, total cholesterol, HDL-cholesterol, LDL-cholesterol, triglycerides (TG), BUN, creatinine, blood glucose, Ca, Na, K, P, Cl
Urinalysis	Occult blood, protein, glucose, urobilinogen
Pregnancy test	Urine hCG or serum hCG

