13.8 Inflammatory marker

C-reactive protein (CRP) will be measured at the medical institution. The date of sample collection and the test results will be entered in the eCRF.

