13.9 Cytokines

The following cytokines will be measured at the central laboratory. Measurement results will not be disclosed until the code breaking after the clinical study has been completed. The date of sample collection will be entered in the eCRF : IL-6, IL-1 β , TNF- α , IL-10, CCL17, CXCL9, MMP-12.

Sample collection and storage will be performed in accordance with the procedures specified separately.

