#### 2.1.2.10.2.7 Changes from baseline in the inflammatory marker (CRP) and cytokines to each time point.

(1) Analysis set : FAS

(2) Analysis item : changes from baseline in the inflammatory marker (CRP) and cytokines (each time point - Day 1)

(3) Time point : Day 1, Day 3, Day 5, at discontinuation/completion of treatment

(4) Analytical method :

- 1) Summary statistics (number of patients, arithmetic mean, standard deviation, median, minimum, maximum) for measured values and changes from baseline in inflammatory marker (CRP), cytokine markers (measured values and log2 log-transformed values of IL-6, IL-1 $\beta$ , TNF- $\alpha$ , IL-10, CCL17, CXCL9, MMP-12) and CXCL9/CCL17 ratios to each time point will be calculated by treatment group and by time point. In addition, a chart for the mean  $\pm$  standard deviation over time will be prepared by treatment group.
- 2) Estimated values of differences between groups, 95% confidence intervals and the p-values (Day 3, Day 5, at discontinuation/completion of treatment) will be calculated using mixed effect model for repeated measures with and changes from baseline in inflammatory marker (CRP) and cytokine markers (measured values and log2 log-transformed values of IL-6, IL-1 $\beta$ , TNF- $\alpha$ , IL-10, CCL17, CXCL9, MMP-12) and CXCL9/CCL17 ratio to each time point as response variables, baseline values as the covariate, time point, treatment group, and time point \* treatment group as the fixed

effects. In addition, a chart for the changes in estimated values and 95% confidence intervals over time will be prepared by treatment group.

2.1.2.10.2.8 Distribution and proportion of patients in each category on a 7-point ordinal scale from Day 0 until Day 28

(1) Analysis set : FAS

(2) Analysis item : 7-point ordinal scale

(3) Time point : Day 0 to Day 28

(4) Analytical method :

1) The number of patients and the proportion in each category on the 7-point ordinal scale shown in Table 2.1 from Day 0 until Day 28 will be summarize by treatment group and by time point (number of patients, %). In addition, a bar chart showing the percentage of each category will be prepared by treatment group and by time point.

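### SAP 4.2 keeps laboratory values in each site's unit without conversion, yet the SAP pools them across sites; locally measured CRP likewise has no common unit

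*SAP*

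**What the plan says.** **Rule on units.** SAP 4.2: "The unit and reference values for the laboratory test and vital signs will be used as those in the institution, and not be converted".

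**Safety laboratory tests.** These are local. Protocol 13.6 says "The following items will be measured at the medical institution". SAP 2.1.2.11.2 then asks for summary statistics "for the measurement values and changes in each parameter of the blood test will be calculated by treatment group and by time point", plus box plots, with no split by site or by unit.

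**CRP.** Protocol 13.8: "C-reactive protein (CRP) will be measured at the medical institution". No unit is given there or anywhere else in the two documents. CRP is the only named inflammatory marker and belongs to secondary endpoint (6) in Protocol 5.2.1: "Changes in inflammatory markers and cytokines from baseline to the end of administration". SAP 2.1.2.10.2.7 fits a repeated-measures model to the change in CRP, with baseline, time point, treatment group and their interaction. The model code in SAP 4.7 has no site or unit term. The log2 transformation is listed in the bracket after the cytokine markers, and CRP stands outside that bracket.

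**Cytokines, for contrast.** Protocol 13.9: "The following cytokines will be measured at the central laboratory". SAP 4.2 gives their quantification limits in pg/mL, so their unit is settled.

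**The concern.** A mean or SD taken over several sites has a meaning only if the numbers share a unit. SAP 4.2 leaves each hospital's unit in place and rules out the step that would align them, while SAP 2.1.2.11.2 averages across hospitals. This is an explicit instruction, not a detail left to good practice: a programmer who follows the SAP to the letter would not convert. If one site reported white cells in 10^3/µL and the rest in /µL, the arm means would mix numbers that differ by a factor of 1000.

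For CRP the question reaches an efficacy endpoint. Reporting in mg/L at one site and mg/dL elsewhere would give a factor of 10, and a change on the raw scale carries that factor into both the treatment difference and the residual variance. Randomization is stratified by standard treatment only (Protocol 10.2), so the arms need not be balanced within a site that uses a different unit.

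**Working it through.** **The plan's own figure.** The only power statement is 82.1% for the log-rank test of the primary endpoint (Protocol 18: normal times with means 10 and 14, common SD 4.5, 40 vs 20). A simulation of 4,000 trials, cut at Day 28, gives 82.7%, so it reproduces. It uses no laboratory value and the present point does not touch it.

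**Direct arithmetic on pooled mean changes.** Let *k* be the ratio of the odd site's unit to the common one, *f* the share of each arm treated at that site, and *D* a mean change that is the same in both arms. Each arm's pooled mean change is D × [1 + (k − 1) f], so

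spurious difference = (k − 1) × (f_active − f_control) × D.

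For a site with 6 of the 60 patients (40 active, 20 control) and k = 10:

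- split 5/1: 9 × (5/40 − 1/20) × D = 9 × 0.075 × D = 0.675 D
- split 6/0: 9 × (6/40 − 0) × D = 1.35 D
- split 3/3: 9 × (3/40 − 3/20) × D = −0.675 D
- split 4/2, the exact 2:1 ratio: 9 × (4/40 − 2/20) × D = 0

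With k = 0.1 the non-zero splits shrink to between 0.068 D and 0.135 D in size. With k = 1000 (the white-cell case) the 5/1 split gives 999 × 0.075 × D, about 75 D. The same formula holds for pooled means of measured values, with D replaced by the mean level.

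**CRP model.** From the documents: 40 vs 20 patients and a two-sided 5% level (Protocol 17.5, 18). Assumed, because the documents give no CRP figures: lognormal baseline with median 8 and log-SD 0.8; post/baseline ratio 0.4 with log-SD 0.6; treatment either has no effect or halves that ratio. Change is regressed on arm and baseline (a single-visit stand-in for the repeated-measures model), with 3,000 trials per row. The odd-unit patients are drawn at random.

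| Patients in odd unit | Factor | Mean estimate | SD of estimate | Power | Rejection with no effect |
|---|---|---|---|---|---|
| 0/60 | – | −2.51 | 1.09 | 86.7% | 5.0% |
| 3/60 | 10 | −3.27 | 1.86 | 73.1% | 4.0% |
| 6/60 | 10 | −4.22 | 2.83 | 63.7% | 4.3% |
| 12/60 | 10 | −6.56 | 4.51 | 59.0% | 4.2% |
| 3/60 | 0.1 | −2.42 | 1.10 | 85.4% | 4.7% |
| 6/60 | 0.1 | −2.33 | 1.04 | 84.7% | 4.6% |
| 12/60 | 0.1 | −2.06 | 0.99 | 80.7% | 4.5% |

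Relative to −2.51, the factor-10 estimates are inflated 3.27/2.51 = 1.3 to 6.56/2.51 = 2.6 times. The factor-0.1 estimates are about 0.8 to 0.95 times the common-unit value. The simulation error on the 80.7% is √(0.807 × 0.193/3000) = 0.7 points; a 20,000-trial repeat gave 81.7%, hence about 82–85% for that direction.

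**Sensitivity to the assumptions.** With a normal baseline instead (mean 9, SD 4, Day 5 residual SD 2), and 10% of patients at factor 10, power fell from 85% to 43%. A separate run of a similar model at factor 0.1 gave 79% against 83%. The direction is stable; the size is not.

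**Log scale.** log2(k·y) − log2(k·b) = log2(y) − log2(b), so a log-scale change would cancel a constant factor. As written, the SAP does not list that transformation for CRP.

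**The case against.** **SAP 4.2 may not reach CRP.** It names laboratory tests and vital signs. The documents keep CRP apart: it has its own section (Protocol 13.8), shares a schedule row with the cytokines rather than with the laboratory tests, and is missing from the laboratory lists in Protocol 13.6 and SAP 2.1.2.11.2. This stands. A reader might infer that the SAP forbids converting CRP; the text supports that only on a broad reading. What is certain is that no common CRP unit is set.

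**No site is shown to differ.** Also right. Results enter one data-capture system under a data entry manual that is not part of these documents (Protocol 20.1), and inconsistent entries are queried (20.2, 22.1). Units may be fixed there, and a tenfold discrepancy could well be caught. SAP version 1.1 is dated December 2021, after the planned study end of October 2021, so the sentence might record that no conversion proved necessary. That is possible, but neither document says it, and wording that speaks of the institution's unit suggests that units may vary. If units were fixed, SAP 4.2 should say so.

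**The harm is not a false positive.** A reader might infer that mixed units would manufacture a treatment effect. Over repeated randomization the null difference averages about zero and the rejection rate is 4–5%. In a single trial a chance imbalance can still produce a spurious difference of the sizes shown, and the reported estimate is on a mixed scale. If the odd site's numbers are the smaller ones, the loss is minor.

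**Weight.** CRP is one component of one secondary endpoint and carries no power claim.

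**Conclusion.** The conflict between SAP 4.2 and the pooled summaries of SAP 2.1.2.11.2 is on the page: values left in local units are averaged as if they had one unit, and neither document requires that they do. For CRP the gap is the absence of a common unit for a pooled raw-scale model.

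The numerical consequence is conditional. It is zero if all sites already share units. Under the lognormal CRP inputs above, which are assumptions, power drops from about 87% to 59–73% when 5–20% of patients carry values ten times larger, or to 82–85% when the values are ten times smaller. Type I error stays near 5%. The documents do not support saying that the CRP result or the safety tables are in fact wrong, only that the written rule would make them so if one site's unit differed. The primary endpoint is unaffected. This is worth correcting because the rule is explicit and the correction is cheap.

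**What to change.** Replace the sentence in SAP 4.2 with one to this effect: *all laboratory values, and CRP, are collected in or converted to one prespecified unit per parameter before any summary statistic, change from baseline, plot or model; institution units and reference ranges are kept only for out-of-range flags and listings.* If the eCRF already fixes the units, state that and list them.

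Site units for the laboratory tests can come from the list of institution reference values already planned in SAP 2.1.2.11.2, item 6). That section's item list does not include CRP, so CRP units must be obtained from the sites or the eCRF.

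Cost: one SAP sentence, a conversion table in the programming, and a check of the CRP unit at each site. No new patient measurements are needed.

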2) For patients who were categorized in each category on a 7-point ordinal scale on Day 14 (or at the last observation the point) and Day 28 (or at the last observation time point between Day 15 and Day 27), the p-values (Wilcoxon's rank sum test) of the differences between groups will be calculated.

2.1.2.10.2.9 Distribution and proportion of patients in each category of oxygen requirement until Day14

(1) Analysis set : FAS

(2) Analysis item : oxygen requirement

(3) Time point : Day 0 to Day 14

(4) Analytical method :

1) The number of patients and the proportion in each category on the oxygen requirement shown in Table 2.2 until Day 14 will be summarize by treatment group and by time point (number of patients, %). In addition, a bar chart showing the percentage of each category will be prepared by treatment group and by time point.

2) For patients who were categorized in each category on the oxygen requirement on Day 5 and Day 14, the p-values (Wilcoxon's rank sum test) of the differences between groups will be calculated.

Table 2.2 Oxygen requirement

Category	Ordinal scale
1	Require oxygen supply of 4 L/min or more using oxygen mask
2	Require oxygen supply of 2 L/min or more using nasal cannulas
3	Require oxygen supply of less than 2 L/min using nasal cannulas
4	Do not require oxygen supply but feel shortness of breath during walking or moving
5	Do not require oxygen supply and do not feel shortness of breath during walking or moving

Table 2.3 Definition of event/censoring in Time to event analysis

Analysis item	Event/ Censoring	Definition of event/censoring	Period

 
Period to the first improvement by at least 2-rank between baseline and Day 28 on a 7-point ordinal scale 
 
Period from baseline to the day of discharge
 
Period from baseline to shifting to Category 6 or 7 on a 7-point ordinal scale
 
Period from baseline to shifting to Category 5 on a 7-point ordinal scale
 
Period to from baseline to improvement by 1 rank or more on a 7-point ordinal scale
 
 
 
	Event	A patient who developed an event	Period until the onset of the first event
	Censoring	A patient who completed the study without any event	Period until the last observation day
		A patient who discontinued or died	Censored after complementing 29 days*

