#### 4.7 SAS Code

- SAS Code for implementing Cox regression model is shown below.

```
ods output ParameterEstimates = [OUTPUT];
proc phreg data = [DATASET];
  class [GROUP] [THERAPY];
  model [TARGET] * [CENSOR FLG](0) = [GROUP] [THERAPY] / rl alpha = 0.05;
run;
```

- SAS Code for implementing MMRM model is shown below.

```
proc mixed data = [DATASET];
  class [SUBJECT] [VISIT] [GROUP];
  model CHG = BASE [VISIT] [GROUP] [VISIT] * [GROUP] /ddfm = KR;
  lsmeans [GROUP]* [VISIT];
  repeated [VISIT]/ subject = [SUBJECT] type = UN;
```

run;

- SAS Code for implementing analysis using generalized estimating equation is shown below.

```
proc genmod data = [DATASET];
  class [SUBJECT] [VOLUME] [GROUP];
  model CHG = [GROUP] [VOLUME] [GROUP]* [VOLUME] ;
  lsmeans [GROUP]* [VOLUME];
  repeated subject = [SUBJECT] type = UN or CS;
run;
```

- SAS Code for implementing analysis using MMRM model (cLDA method) is shown below.

\* The coefficient of Estimate must be changed to suit the data.

\*The value of DIF3, DIF5, and DIF10 in the active group is 1 at each time point, otherwise 0.

```
proc mixed data = [DATASET] order = internal;
  class AVISITN(ref = "1") USUBJID;
  model AVAL_ = AVISITN DIF3 DIF5 DIF10/noint s ddfm = kr;
  random USUBJID;
  /* difference between groups in each time point*/
  estimate "Diff (NPC-26 - Placebo) Day3" DIF3 1 /cl;
  estimate "Diff (NPC-26 - Placebo) Day5" DIF5 1 /cl;
  estimate "Diff (NPC-26 - Placebo) Day10" DIF10 1 /cl;
  /* Mean CHG in each time point in each group */
  estimate "LSMean of Change from BL (Placebo) Day3" AVISITN 1 0 0 -1 /cl;
  estimate "LSMean of Change from BL (Placebo) Day5" AVISITN 0 1 0 -1 /cl;
  estimate "LSMean of Change from BL (Placebo) Day10" AVISITN 0 0 1 -1 /cl;
  estimate "LSMean of Change from BL (NPC-26) Day3" AVISITN 1 0 0 -1 DIF3 1 /cl;
  estimate "LSMean of Change from BL (NPC-26) Day5" AVISITN 0 1 0 -1 DIF5 1 /cl;
  estimate "LSMean of Change from BL (NPC-26) Day10" AVISITN 0 0 1 -1 DIF10 1 /cl;
  /*Mean AVAL in each time point in each group */
  estimate "LSMean (Placebo) Day1" AVISITN 0 0 0 1 /cl;
  estimate "LSMean (Placebo) Day3" AVISITN 1 0 0 0 /cl;
  estimate "LSMean (Placebo) Day5" AVISITN 0 1 0 0 /cl;
  estimate "LSMean (Placebo) Day10" AVISITN 0 0 1 0 /cl;
  estimate "LSMean (NPC-26) Day1" AVISITN 0 0 0 1 /cl; *This is same as in common with
Placebo;
  estimate "LSMean (NPC-26) Day3" AVISITN 1 0 0 0 DIF3 1 /cl;
  estimate "LSMean (NPC-26) Day5" AVISITN 0 1 0 0 DIF5 1 /cl;

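### Out-of-range cytokine values are set to the assay limit and analysed as exact, which attenuates log2 treatment differences, makes their 95% intervals under-cover and can bias the CXCL9/CCL17 ratio in either direction

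*SAP*

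**What the plan says.** Change in inflammatory markers and cytokines is secondary efficacy endpoint (6) in Protocol 5.2.1. Seven cytokines are measured at a central laboratory (Protocol 13.9).

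For results outside the quantification range, SAP 4.2 states that "the following lower limit and upper limit will be complemented" and lists a pair of limits for each marker, for example "IL-6 : 4.07 pg/mL - 990.00 pg/mL" and "IL-10 : 12.72 pg/mL - 1030.00 pg/mL". The SAP uses the same verb for filling in a value in Table 2.3 ("Censored after complementing 29 days"), so the natural reading is that a result below the lower limit (BLQ) becomes the lower limit and one above the upper limit (ALQ) becomes the upper limit.

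SAP 2.1.2.10.2.7 summarises measured values, log2 values and the ratio: "CXCL9/CCL17 ratios to each time point will be calculated by treatment group and by time point". It then models changes with "CXCL9/CCL17 ratio to each time point as response variables, baseline values as the covariate", reporting group differences, 95% intervals and p-values. The code in SAP 4.7 is an ordinary Gaussian model, "model CHG = BASE [VISIT] [GROUP] [VISIT] * [GROUP] /ddfm = KR", with no censoring term. SAP 2.1.2.14 covers measurement error, unexplained abnormal values, missing data and blood gases, but not results outside the assay range. No sensitivity analysis and no table of the out-of-range share is planned.

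**The concern.** A value known only to lie below a limit is treated as if it had been measured at that limit. A patient who is BLQ at both visits gets a change of exactly zero. A fall that crosses the limit is cut off there. The residual spread shrinks as well, so the interval is both off-centre and too narrow.

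The direction matters in this trial. Protocol 4.1 presents the drug as damping cytokine storm and lung inflammation, so for inflammatory cytokines the hoped-for effect is a fall. A fall moves the active arm further into the BLQ range and loses more of the effect than a rise of the same size would. Without a table of out-of-range shares, a reader could not tell a null cytokine result from a clipped one.

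The ratio is a separate problem, because clipping one component but not the other can create a difference that does not exist.

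**Working it through.** **Nothing to reproduce.** The documents give no out-of-range share, SD or expected effect for any cytokine. The only power figure, 82.1% in Protocol 18, concerns the primary endpoint and has no bearing here.

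**Inputs from the documents.** Limits from SAP 4.2; 40 active and 20 control from Protocol 18; change from baseline with baseline as covariate from SAP 2.1.2.10.2.7 and 4.7; two-sided 5% from SAP 2.1.2.12. The IL-6 limits span 990/4.07 = 243-fold and the IL-10 limits 1030/12.72 = 81-fold.

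**Assumptions.** Log2-normal values, SD 2, correlation 0.6 between baseline and the later visit, control mean unchanged (set to 0), true difference -1 (a halving), and 10 to 60% BLQ at baseline. One post-baseline visit with complete data stands in for the repeated-measures model.

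**Step 1, expected attenuation.** With limit L, mean μ, SD σ and z = (L - μ)/σ, the mean of a clipped normal variable is

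E[max(Y, L)] = L·Φ(z) + μ·(1 - Φ(z)) + σ·φ(z).

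Randomisation balances the baseline covariate in expectation, so the adjusted difference targets the difference between these two means. At 40% BLQ, L = 2 × (-0.2533) = -0.507.

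- Control: -0.507 × 0.400 + 0 + 2 × 0.3863 = 0.570
- Active: -0.507 × 0.597 - 1 × 0.403 + 2 × 0.3870 = 0.069
- Difference: 0.069 - 0.570 = -0.50, against a true -1

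The same formula gives -0.85, -0.72 and -0.31 at 10, 20 and 60%. The active-arm BLQ share at the later visit is Φ((L + 1)/2) = 22, 37, 60 and 77% at the four settings.

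**Step 2, coverage and power.** Simulated trials, 2,500 or more per cell, with clipped values in the ANCOVA; repeat runs agreed to within about 0.02 in the estimate and two points of coverage:

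| BLQ at baseline | Estimate (true -1) | Coverage of 95% CI | Power |
|---|---|---|---|
| 0% | -1.00 | 94% | about 60% |
| 10% | -0.85 | 93% | 57% |
| 20% | -0.71 | 85% | 55% |
| 40% | -0.50 | 52% | 48% |
| 60% | -0.30 | 10% | 37% |

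**Step 3, other assumptions** (log2 SD 1.5, correlation 0.5; shares are for controls):

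| True shift | BLQ | Estimate/true | Coverage |
|---|---|---|---|
| +0.5 SD | 30% | 0.78 | 93% |
| +0.5 SD | 50% | 0.59 | 80% |
| +0.5 SD | 70% | 0.40 | 37% |
| -0.5 SD | 10% | 0.85 | 93% |
| -0.5 SD | 30% | 0.61 | 75% |
| -0.5 SD | 50% | 0.39 | 31% |
| -1 SD | 20% (56% active) | 0.63 | 37% |

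With no true difference there was no bias, and the rejection rate stayed at about 5% or below.

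**Step 4, pg/mL scale** (IL-6 limits). The effect is milder. For +0.5 SD with 50% BLQ, coverage is 93%. For -1 SD with 50% BLQ it is 56%, but it is already 81% with no clipping at all, so part of that shortfall comes from skewness. Coverage fell below 50% only for -1 SD with 80% BLQ (28%).

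**Step 5, ratio.** If both chemokines are BLQ, the ratio is 709.14/104.40 = 6.79, a property of the assay and not of the patient. Now let both markers shift equally, so that the true log2 ratio difference is 0, with only the numerator 50% BLQ:

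- Both fall 0.75: estimate +0.46, false-positive rate 22%
- Both fall 1.5: estimate +1.04, false-positive rate 72%
- Both rise 1.5: estimate -0.47, false-positive rate 16%

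These are for the log2 ratio. The SAP names the ratio outside the bracket that lists log2 values, so its intended scale is unclear.

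**Step 6, a censored likelihood.** Under the Step 2 assumptions, a Tobit ANCOVA at 20 to 60% BLQ gave estimates between -0.93 and -1.04 with coverage 92 to 95%. Under no effect its rejection rate was 5 to 7% (250 trials per share).

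**The case against.** The rule is prespecified, identical in both arms and tied to an assay validation report. The harm depends on a share that nobody can read from the documents: at 10 to 20% BLQ with a modest effect, coverage stays at about 85 to 95%. That stands, and it is why the sizes above are a range and not a prediction.

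Two stronger readings are tempting. One is that the intervals miss the true difference most of the time. In the Step 2 grid that happens only at 60% BLQ. A larger assumed fall brings it on at lower shares (Step 3, last row), but the documents supply neither the share nor the effect. The other is that clipping always shrinks differences or produces false positives. Neither is general: a single cytokine with no effect keeps its error rate, while the ratio can move away from zero.

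The Tobit comparison is favourable to Tobit, since the data came from the model it assumes, with one visit and no missing values. A full censored mixed model over several visits at 40 versus 20 was not tested, and at high BLQ shares any such fit leans on an unobserved tail. This supports a per-visit model over a more elaborate one, and keeping the planned model alongside.

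Setting the ratio to missing when a component is out of range might look like a simple repair. It selects on outcome. With only the numerator censored and a true log2 ratio difference of -1, it gave -0.65 against -0.71 under the SAP rule at 20% BLQ, and cut the analysable patients from 60 to about 37. At 40% it gave -0.55 against -0.50, with about 22 left.

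**Conclusion.** The point holds for the log2 cytokine analyses and the ratio. For a single cytokine, limit substitution attenuates a real difference, narrows its interval and costs power. Under the stated assumptions this runs from slight (-0.85, 93% coverage at 10% BLQ) to severe (-0.30, 10% coverage at 60% BLQ). The direction follows from the rule itself; the size rests on the assumed SD, correlation, effect and out-of-range share, none of which is in the documents. The ratio can be biased in either direction and can show a difference where none exists.

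A reader might infer that endpoint (6) as a whole, or the trial's main conclusion, is unsafe. The documents do not support that. SAP 4.2 sets no substitution rule for CRP, which is the other part of the endpoint, the pg/mL analyses are less affected, and the primary endpoint does not use these data. The change should be made, but it is not critical to the primary result.

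**What to change.** 1. Report the BLQ and ALQ share by marker, arm and visit.
2. For the log2 analyses, fit a censored-normal (Tobit) ANCOVA at each visit, with BLQ left-censored and ALQ right-censored, and with the baseline value plus a baseline-BLQ indicator as covariates. Make it the main estimate, or at least a prespecified sensitivity analysis beside the limit-substituted model. Substitution can stay for the summary tables.
3. For markers with most values out of range, compare detection rates or ranks instead.
4. State the scale of the CXCL9/CCL17 analysis. Analyse the log2 ratio with its components treated as censored: a BLQ numerator bounds the ratio from above, a BLQ denominator bounds it from below, and two BLQ components give no bound. Treat such ratios neither as exact nor as missing.

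The cost is SAP wording and moderate programming. Intervals will be wider, the estimates rely on log-normality when the BLQ share is high, and a marker with few quantifiable values may support only a detection-rate comparison.
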